5. Please list all Research Sites in addition to Louis Stokes Cleveland DVA Medical Center (LSCDVAMC); The Cleveland VA is our site. [name] at Duke University and the Durham VA will also be funded by Merck and run 30 subjects there. He will send us coded blood samples to analyze with our samples. His samples will come from the Duke University site not their VA.

International studies when the PI is the Lead Investigator list the countries:

a. When study procedures including analysis of identifiable samples or data involving LSCDVAMC enrolled subjects will be conducted at any site other than the LSCDVAMC please provide the following:

Name and contact information for the site:

Describe the plan for communicating protocol amendments, reports of serious adverse events, reports of unanticipated problems involving risks to subjects or others, interim reports, and DSMB reports to external sites.

* When the LSCDVAMC is considered the coordinating center and the PI the lead investigator on cooperative research or a multi-center trial contact AO/Research [contact].

6. Sponsor or other Support (list industry sponsor, government support, etc.):

Merck

Section 3 – Research Design and Procedures

7. Definitions- Provide a list of all abbreviations and specialized terms to be used in this document and their definitions:

Abbreviations / Specialized Terms (Use the Enter key in this column to insert additional abbreviations and their definitions)	Definition
LSCDVAMC	Louis Stokes Cleveland DVA Medical Center
VZV	varicella zoster virus
HZ	Herpes Zoster
CMI	cell mediated immunity
ZOSTAVAX	Trade name for the shingles vaccine
XRT	X-Ray Therapy
chemo	chemotherapy

8. Provide a BRIEF SUMMARY of the background for this research. DO NOT CUT and PASTE paragraphs that do NOT summarize the background.

- *Include a critical evaluation of existing knowledge, and specifically identify the information gaps that your protocol is intended to fill.*
- *Refer to appropriate citations in the scientific literature and include your references at the end of this section.*
- *Include the rationale for conducting the research at the VA.*

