A portion of the sample may be sent to our collaborators at University of Pennsylvania (Drs. [name] and [name]), or Vaccine and Gene Therapy Institute in Port-St-Lucie, FL ([name], coming to CWRU this Fall to join our faculty), and Merck's immune assay unit (Swiftwater, PA) as each of these collaborators perform assays that we do not perform at the VA in the [name] laboratory. Any samples that are sent will be coded with no personal identifiers. The cells going to Penn will have advanced T cell marker analysis and cloning, to [name] they will have transcriptomic analysis, and to Merck they will have anti-VZV glycoprotein ELISA performed. Samples will be destroyed in Cleveland and at the other sites after the assays are performed.

11. Provide a BRIEF DESCRIPTION of how the estimated number of study subjects needed for this research was determined

- *If this is a quantitative study provide the method of determining sample size estimates.*
- *If multiple studies are planned provide a power analysis or justification for each one.*

This is a pilot study so precise sample size calculations are not possible since the data do not exist yet to determine this. Obtaining this pilot data is one of the key purposes of this study. For the primary analysis: If we anticipate some loss of subjects for various reasons beyond our control so that we hope to end up with about 76 subjects for full analysis after initially enrolling 90 subjects. This is based a projection of receiving up to 30 coded samples from our collaborator [name] at Duke University who is running a similar study at that site and initially enrolling 60 from Cleveland. Using G*Power to perform a sample size calculation with 76 subjects (38 vaccinated and 38 un-vaccinated assuming some loss due to lack of all 4 timepoints) and an analysis comparing these two groups at the 3 time points to test Hypothesis 1 using a 2 x 3 Repeated Measures ANOVA with power 0.8 and α error 0.05 we can detect an effect size of 0.27. For independent t-tests analyzing mean differences at each individual time point we would be able to detect an effect size of 0.58. For both of these types of analyses our power is near a medium effect size. The data from this pilot study will inform the sample size for a larger future study.

12. The research involves the following procedures conducted by and for what purpose:

[figure not shown]
PROCEDURE	PERFORMED BY:		PROCEDURE IS:	

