Surgical procedure or Specimen removal during surgery				
Tissue banking (complete Section 12)				
Use of pre-existing tissues/specimens				
Other (list):				

- **Standard of care procedures are procedures performed in the course of normal medical care.*
- ***Research Procedures are performed for the purposes of this research alone.*

13. Please describe the research design and all study related procedures.

- Describe ALL PROCEDURES ASSOCIATED WITH THIS RESEARCH. This includes standard of care and research procedures.
- For complex studies please include diagrams and tables. Be sure to describe when each procedure will be performed. Be sure to provide information for each cohort, including normal controls.

Study participants based on the inclusion and exclusion criteria listed below will be recruited from the Oncology clinics and medical services of the Cleveland VA. The study oncologist will review the study with them. Subjects that consent will be randomized to one of the two arms, vaccine or no vaccine. Individuals will undergo blood draws for immunologic assays according to time points depicted in the figure below. Each blood draw (25 ml each) has been timed to follow routine clinical monitoring as ordered by the oncologist for maximum feasibility.

- The first blood draw will be at the time of consent into the study. We anticipate this time to be the first visit with the oncologist. They will receive ZOSTAVAX on that day if they are in that arm of the study.
- The second blood draw will be on the day of chemotherapy initiation, no earlier than 14 days post-vaccination. This will be longer than 14 days for example when there is surgery between the vaccination and the start of chemotherapy.
- The third blood draw will be at the start of the second chemotherapy cycle.
- The fourth blood draw will be 3-24 months post chemotherapy cessation. The timing of the final blood draw is based on cessation of chemotherapy and not any concurrent radiation therapy that would be also completed by the 3-6 month post-chemotherapy sampling.

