The subjects chemotherapy is decided by the Oncologist and/or Tumor Board in consultation. The duration of chemo similarly is also decided clinically. If the patient needs surgery or XRT

as part of the therapy, it is decided on entirely by the clinicians. The study is working around all of these clinical decisions.

Subjects will be called between visit 2 and 3 and then between visits 3 and 4. They will be asked if they had a side effects or event that may have been serious since the last study visit or telephone contact. They will also be asked if they were exposed to anyone who has chickenpox or shingles, and if they had any symptoms of shingles.

For 4 weeks after they receive their shot, they will be asked to record information about potential vaccine side effects on the vaccination Report Card.

14. Will the research involve the following?

N/A Chart/Data Review

Placebo Group No Yes (describe):

Other Control Group No Yes (describe): The control group is persons that do not get the vaccine.

Randomization No Yes (describe): We will obtain clinical information to determine eligibility this includes meds and PMH and then follow the subject's clinical course to know when to do the subsequent sampling. We will use a cloud based randomized tool to generate the list before the start for the whole study for what the order of vaccine or no vaccine will be. We will then have paperwork packets in the order of enrollment premade. We will open each packet at the consenting time and find vaccine or not and enroll and begin the study.

Deception No Yes (describe):

15. Does the research involve the use and/or disclosure of Individually Identifiable Health Information in any form or medium?

No Yes If yes, complete the required HIPAA Waiver/Authorization forms.

16. Does the study include the administration of a study agent that does not require FDA approval and does not require an IND (e.g. vitamins, food supplements, isotope tracers, alternative medicines, etc.)?

No Yes -provide a detailed description of the procedures used to assure patient safety:

17. Will radioactive material be administered or will subjects be exposed to ionizing radiation?

• Ex. Radiographic equipment, fluoroscopic equipment, and CT scanners, etc.

No Yes

18. In your judgment, could the objectives of the research be met in a way that presents less risk to subjects?

No Yes please explain:

Section 4 – Subject Selection, Recruitment, and Vulnerable Populations

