30 ZOSTAVAX

30 no vaccine

The Duke University site will have 15-ZOSTAVOX and 15 no vaccine

N/A SINGLE SITE

22. Duration of individual subject participation

Provide answers for each cohort including normal controls; (patients, family members, treating physicians,). 5 years or less depending on the duration of their chemo.

Chart/record review N/A

23. Age range of subjects

- provide answers for each cohort, including normal controls:

Adults 18 years or greater

Specific age range (list age range): 50 years and older for both cohorts

Children –waiver from VACO: attached pending- provide submission date:

**Contact AO/Research [contact] for guidance..

24. Which of the following will be recruited or reviewed for this study (check all that apply)?

Veteran Inpatients

Men

Veteran Outpatients

Women

Veteran Families

*Normal volunteers

*Non-Veterans; Provide justification

*According to VHA Handbook 1605.04 Notice of Privacy Practices VHA must provide a copy of its VHA Notice of Privacy Practices to all non-Veteran patients (e.g., active duty personnel or those seeking care in humanitarian circumstances) receiving care or treatment at a VHA health care facility or non-Veteran research subjects enrolled in an approved VHA research study with clinical trials. VA Form 10-0483 Acknowledgement of the Notice of Privacy Practices should be signed by the non-Veteran research subject at the time of consent and given a copy of the Notice of Privacy Practices. Once the Acknowledgement Form is signed please send a copy to the Privacy Officer. If additional information is needed please contact your Facility Privacy Officers [name] or [name] [contact] / [contact] [contact] / [contact].

25. Which vulnerable population(s) will be TARGETED for recruitment in this study:

- Indicate only those populations that are specifically targeted for the research described in this document.
- *It is not necessary to check any box if, for example, your study will include a full range of subjects, some of whom may be elderly or subjects who might incidentally be employees.*

- N/A Chart Review (proceed to Item 30)
- NONE (proceed to Item 26)
- Medical students, house staff, or Employees of the VAMC or Case
- Pregnant Women OR Women who are Breastfeeding, Human Fetuses, or Neonates
- Children – Complete Section 14 “Children as Research Subjects”
- Prisoners (The LSCDVAMC does not conduct research involving prisoners)
- Targeting Persons over Age 65

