## 2.7 Statistical Analysis and Sample Size Justification

This study is a pilot protocol. Our goal is to enroll a total of 90 subjects (30 Duke, 60 Cleveland).

For the primary analysis: If we anticipate a loss of up to 15% of subjects for various reasons beyond our control so that we will end up with about 76 subjects for full analysis. Using G\*Power to perform a sample size calculation with 76 subjects (38 vaccinated and 38 un-vaccinated) and an analysis comparing these two groups at the 3 time points to test Hypothesis 1 using a 2 x 3 Repeated Measures ANOVA with power 0.8 and  $\alpha$  error 0.05 we can detect an effect size of 0.27. For independent t-tests analyzing mean differences at each individual time point we would be able to detect an effect size of 0.58. For both of these types of analyses our power is near a medium effect size. We do not have preliminary data in this population for a precise sample size calculation. The data from this pilot study will inform the sample size for a larger future study.

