Fold change will be the primary immune analysis and will be calculated for each individual subject based on their day 0 SFU on ELISPOT. Fold change will be calculated at each time point (chemo initiation, during chemo, 3 months post). This will take place in both the vaccinated and non-vaccinated groups. As this model reflects a 2 group by 3 time point design, our initial overall assessment of the data will use a 2X3 Repeated Measures ANOVA (RMANOVA) to identify mean differences between groups, within time mean differences, and the interaction between groups and time to identify if the trends in the means over time is different for groups (vaccine vs. no vaccine). For the next step to gain a better understanding of how well the vaccine works at each time point (Hypothesis 2-4), we will use independent samples t-tests to analyze group mean differences at each time point separately to gain a better understanding of how the groups may be different at chemotherapy initiation, during chemotherapy, and at 3 months post-chemotherapy. Additionally, if we identify a significant interaction between group and time points, we will run follow-up RMANOVAs for each group separately to identify not only mean difference over time, but also linear (e.g. a steady increase or decrease in mean scores over time) and quadratic (e.g. a high mean scores at chemotherapy initiation, followed by a decline in mean score during chemotherapy, followed by a steady increase in mean score at 3 months post-chemotherapy) trends in the means over time for each group. Violations of the assumptions for each analysis will be tested and the data will be transformed or the nonparametric equivalence analysis will be used when appropriate.

[name] is the director of the Cleveland VA's core statistical center. He is an ongoing Co-investigator with effort on one of [name] R01 grants. He will perform the statistics for this study.

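### Two sites are pooled, but neither the randomisation description nor any planned model includes site; if mean fold change differs by site, the group comparison loses efficiency that one model term would recover.

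*Protocol*

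**What the plan says.** **Sites.** SAP 2.7 sets a goal of 90 subjects, 60 from Cleveland and 30 from Duke. Protocol item 5 says of the Duke collaborator: "His samples will come from the Duke University site not their VA". It adds that his coded blood will be analysed alongside Cleveland's. Protocol item 11 describes Duke as running a similar study.

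**Numbers per arm.** Protocol items 20 and 21, which ask for estimated numbers of subjects, give 30 vaccine and 30 no vaccine at Cleveland, and "The Duke University site will have 15-ZOSTAVOX and 15 no vaccine".

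**Randomisation.** Protocol item 14 uses a cloud tool to "generate the list before the start for the whole study for what the order of vaccine or no vaccine will be", with packets opened in enrolment order. It describes no blocking, no stratification and no site-specific list. It does not say whether the list covers Duke.

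**Analysis.** In SAP 2.7, "our initial overall assessment of the data will use a 2X3 Repeated Measures ANOVA" on fold change from each subject's own day 0 ELISPOT count. Independent-samples t-tests at each time point follow. Protocol item 10 says the same. Neither document mentions site in the analysis.

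**Stated power.** Both documents work from "76 subjects (38 vaccinated and 38 un-vaccinated"). Protocol item 11 says that for the "2 x 3 Repeated Measures ANOVA with power 0.8 and α error 0.05 we can detect an effect size of 0.27". SAP 2.7 adds: "For independent t-tests analyzing mean differences at each individual time point we would be able to detect an effect size of 0.58".

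**The concern.** A VA population and a university population may respond differently to the vaccine or to chemotherapy. If so, part of the variation in fold change lies between sites, and an analysis without site counts it as error.

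Two situations are possible, and both call for a site term. If 15/15 and 30/30 are achieved, the site difference cancels from the arm contrast, but the unadjusted standard error still contains it, so the test is conservative. If they are not achieved, chance imbalance at Duke carries part of the site difference into the arm contrast, and nothing corrects it.

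The pilot is also meant to inform the sample size of a larger study. An SD pooled over sites would overstate the within-site SD that a site-adjusted trial needs.

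**Working it through.** **1. The plan's own figures.** Inputs: 38 per arm, α = 0.05, power 0.80 (SAP 2.7). Sidedness and the correlation among repeated measures are not stated.

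- t-test, noncentral t with 74 df and noncentrality d√(38/2): the detectable d is 0.576 one-sided and 0.651 two-sided. The stated 0.58 therefore matches a one-sided test (power 80.5%). Two-sided power at 0.58 is 70.4%. Below, d = 0.651 is the two-sided reference because it starts at 80%.
- RMANOVA group effect, λ = f²·N·m/(1+(m−1)ρ), with N = 76, m = 3 and ρ = 0.5 assumed: the detectable f is 0.266, and power at 0.27 is 81.2%. The stated 0.27 is reproduced.

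**2. Assumed site difference.** Let D be the Duke-minus-Cleveland difference in mean fold change, in within-site SD units. Take 25 Cleveland and 13 Duke subjects per arm, close to the 2:1 enrolment. The variance the unadjusted test uses is then inflated by 1 + (13/38)(25/38)D² = 1 + 0.225D². The SE factor is its square root: 1.007 at D = 0.25, 1.028 at 0.5 and 1.107 at 1.0.

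**3. t-test with exact balance within site** (simulation, 40,000 trials per setting, two-sided, d = 0.651):

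| D | Type I error, no site | Power, no site | Power, site in model |
|---|---|---|---|
| 0 | 5.1% | 79.9% | 79.9% |
| 0.25 | 4.7% | 79.6% | 80.0% |
| 0.5 | 4.4% | 78.2% | 79.9% |
| 1.0 | 3.1% | 73.5% | 80.2% |

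One-sided at the plan's d = 0.58, power without and with site is 79.3% and 80.6% at D = 0.5, and 74.7% and 80.3% at D = 1.0.

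**4. t-test without site-balanced allocation.** The site difference is now real noise in the arm contrast. With a one-third Duke share the inflation is 1 + (1/3)(2/3)D², which is 1.014, 1.056 and 1.222. Noncentral-t power is 79.4%, 77.8% and 71.7%. Type I error stays at 5.0%, even at D = 1.0.

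**5. How far Duke could drift.** Take 45/45 overall and 30 Duke subjects placed at random on an unblocked list. The hypergeometric probability that Duke splits 19/11 or worse is about 12%. Under simple randomisation it is about 20%. A 19/11 split at Duke shifts the unadjusted arm difference by (19/45 − 11/45)D = 0.178D, which is 0.09 SD at D = 0.5 and 0.18 SD at D = 1.0.

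**6. RMANOVA.** The variance of a subject's mean over three times is (1 + 2×0.5)/3 = 0.667 with ρ = 0.5. A constant site shift adds 0.225D² and is not averaged down. For f = 0.27 (a difference of 0.54 SD), power of the group test without site is 80.4% at D = 0.25, 78.0% at 0.5 and about 69% at 1.0. With site it is 81.2% throughout. These figures add the site variance to the noise, as in step 4; under exact balance the loss would be somewhat smaller. A constant shift drops out of within-subject contrasts, so the time and group-by-time tests do not change.

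**7. Cost if the sites do not differ.** One df of 74. RMANOVA power goes from 81.20% to 81.18% with balance. Without balance, the t-test loses about half a point at most.

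**The case against.** The documents give no site mean, SD or intraclass correlation, so any loss is conditional. Three features should limit a site effect: Duke samples are assayed with Cleveland's, fold change from own day 0 removes a proportional site difference in baseline level, and transformation is planned where assumptions fail. At 0.25 SD the t-test loss is under half a point with balance. Omitting site neither inflates type I error nor, under randomisation, biases the comparison on average, and this is a declared pilot. All of this stands and limits the size of the point. It does not remove a site difference in response to vaccine or chemotherapy, and it gives no reason to leave site out.

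Three stronger readings are tempting and are not supported.

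- A reader might infer that allocation is fixed at 15/15 by design and that the analysis throws away precision worth 5–18% of the sample. The head-counts are estimates, and no allocation rule enforces them. The 5–18% comes from inflation of 1.056–1.222, which describes allocation not balanced by site. With balance, the estimate loses no precision; only its standard error is overstated.
- A reader might infer that the sites are known to be very different and that power is therefore lost. The only population difference stated is VA versus university.
- Protocol item 13 says of the interval to the second draw: "This will be longer than 14 days for example when there is surgery between the vaccination and the start of chemotherapy". A reader might infer that planned surgery must also be a covariate. Its effect cannot be sized from the documents, and they do not show that planned surgery is recorded at entry.

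**Conclusion.** The point holds as a conditional loss of efficiency. Site is absent from the randomisation description and from every planned model. For the t-tests the power cost is about 1 point or less at a 0.25 SD site difference, about 2 points at 0.5 SD and 6–8 points at 1.0 SD. For the RMANOVA group test it is about 1, 3 and 12 points. The site difference is assumed throughout, and the RMANOVA figures also assume ρ = 0.5. The time and group-by-time tests are affected only if the site effect changes over time. The point deserves action because the remedy costs almost nothing when the sites do not differ. At small to moderate site differences, the unstated sidedness behind d = 0.58 matters more (70.4% two-sided against 80.5% one-sided) and should be settled separately.

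**What to change.** - **Model.** In SAP 2.7 and Protocol item 10, add site as a fixed between-subject factor to the RMANOVA. Replace each time-point t-test with a linear model containing arm and site, and report the adjusted arm difference with its 95% CI. State that site enters as a main effect without an arm-by-site term, and whether site-by-time is included. If the nonparametric fallback is used, choose a version stratified by site.
- **Randomisation.** In Protocol item 14, state that the tool produces a separate blocked list for each site, so that 30/30 and 15/15 are delivered rather than hoped for.
- **Reporting.** Give the within-site SD of fold change for planning the larger study.
- **Surgery.** Leave it out of the model unless planned surgery is recorded at entry.

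The cost is a few lines of text and one degree of freedom. Site is known for every subject.

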***Certificate of Confidentiality:**

- Certificates of Confidentiality are issued by the National Institutes of Health (NIH) to protect identifiable research information from forced disclosure.
- They allow the investigator and others who have access to research records to refuse to disclose identifying information on research subjects in any civil, criminal, administrative, legislative, or other proceeding, whether at the federal, state, or local level.
- Certificates of Confidentiality may be granted for studies collecting information that, if disclosed, could have adverse consequences for subjects or damage their financial standing, employability, insurability, or reputation.
- By protecting researchers and institutions from being compelled to disclose information that would identify research subjects, Certificates of Confidentiality help achieve the research objectives and promote participation in studies by assuring confidentiality and privacy to subjects.
- For more information, see <http://grants1.nih.gov/grants/policy/coc/index.htm>.

39. Is this project principally concerned with the collection of sensitive information such as sexual attitudes, use of drugs or addictive products, and illegal conduct that would need to be protected against subpoena or forced disclosure in order to protect subjects?

No

Yes- will an application for a *Certificate of Confidentiality be submitted to the National Institute of Health upon IRB approval (or approval contingent on the issuance of such a certificate)?

Yes No provide a justification as to why a Certificate of Confidentiality will not be obtained:

40. Describe all procedures that minimize risks, please include study and standard of care procedures:

We will screen the subjects carefully for any contraindications to the vaccine. Administration of the vaccine will be performed by trained and experienced personal either on the study staff or the clinical nursing staff that gives this standard of care vaccine. Blood draws also will be obtained by the study staff or trained clinical staff. In terms of privacy, interactions with the subjects will occur in private.

41. Describe alternative procedures or course of treatment, if any, which might be advantageous to the subject. State if no alternatives exist or if this is not a treatment study.

The only alternative is not to receive the vaccine and defer it until later from their primary provider.

Minimal Risk: Minimal risk means that the risks of harm anticipated in the proposed research are not greater, considering probability and magnitude, than those ordinarily encountered in daily life or during the performance of routine physical or psychological examinations or tests.

42. Please give your overall risk classification for the research:

- Minimal Risk
 Greater than Minimal Risk

43. Will subjects receive any direct benefit from this research?

- No Yes -describe the direct benefits: They may get benefit from receiving the shingles vaccine that would protect them from an acute zoster outbreak.

44. Please explain briefly why you consider the risks associated with the study to be reasonable in relation to its benefits?

We believe the risks of this FDA approved vaccine are minimal but they do not exactly meet the very strict definition of minimal risk provided above in the yellow box. ZOSTAVAX is an attenuated live virus vaccine so it is not part of "routine physical or psychological examination or test" rather it is something being given. We are using it in accord with the FDA package insert however. Also it is a very safe and low risk vaccine as well. We will carefully review the subjects for contraindications to further minimize any risk.

Section 6 – Informed Consent

45. Type and number of Consent-

- *When more than one consent form is being used a descriptor MUST be in the header section describing the population and/or phase of the study:*
- Written Informed Consent –number used in this study 1**
- *Oral Script/Letter/Information Sheet- number used in this study *Submit Request for Consent Waiver Form-waiver of documentation of informed consent**
- No informed consent at all in this study- Submit a Request for Consent Waiver Form-waiver of informed consent and proceed to item 53**

46. Will all adult subjects have the capacity to give informed consent?

- Yes No- Describe range of impairment.

- *Research involving more than minimal risk, capacity should be determined by a psychiatrist, clinical psychologist, or other qualified professional not otherwise involved in the research.*
- *Individuals who lack the capacity to consent may participate in research only if a legally authorized representative gives consent on their behalf.*

We will review the medical record and if there is concern about the subject's capacity we will talk with the subject's primary physician and team to help us assess their capacity. Many older

persons in particular already have evaluations on the chart discussing capacity. It is not feasible for us to send all subjects for a capacity evaluation and still meet the strict time parameters of 14 days between vaccination and treatment.

47. Will anyone other than the subject be authorized to provide consent or permission for the subject's involvement in the research?

- *e.g., parents, court ordered guardian, spouse, etc.*

No Yes -please explain:

48. Describe how and where informed consent will be obtained:

Consent will be obtained in the VA exam room or hospital room of the subject. The subject will be given the consent and have time to read it. They will also have the study explained and allow time for the study staff to answer questions. The research team will then question the subject about the key elements of the study to assure they understand it.

49. Will there be an opportunity for potential subject to take the consent form home to discuss participation and options with family members?

Yes No - please explain:

It is not possible to take the consent home in virtually all cases as the subject will not have sufficient time to fit into the 2 week time window between the shot and chemotherapy if they take the consent home.

50. List by role who will be obtaining informed consent from subjects or their legally authorized representatives:

- *ex. study coordinator, co-investigator, research nurse, research assistant, PI*

All members of the study team are authorized to obtain consent.

51. Please describe how informed consent will be obtained from subjects who do not read or understand English;

- *identify any languages likely to be encountered, and attach a copy of a translated and authenticated informed consent document*
- *It is appropriate to indicate that you do not anticipate encountering potential subjects who do not speak English based on the population to be studied*

We will exclude those that do not understand English. If they cannot read we can read the whole consent to them.

52. Describe who (by Role ex. PI, Coordinator, etc.) and how it will be determined that subjects and/or legally authorized representative understand the research and their rights.

- *ex. question and answer, repeat back parts of the research, describe a procedure...etc*

Any member of the study team is able access this. The study staff will explain the study when consenting the subject and then go over key elements and have the subjects describe back what they understand will happen in the study.

Section 7 – Privacy and Confidentiality

Privacy - refers to a person's desire to control the access of others to themselves. For example, persons may not want to be seen entering a place that might stigmatize them, such as a pregnancy counseling center that is clearly identified as such by signs on the front of the building. Privacy concerns people, whereas confidentiality concerns data. The research proposal should outline strategies to protect privacy including how the investigator will access information about potential subjects.

In developing strategies for the protection of subjects' privacy, consideration should be given to:

- Methods used to identify and contact potential subjects
- Settings in which an individual will be interacting with an investigator
- Appropriateness of all personnel present for research activities
- Methods used to obtain information about subjects and the nature of the requested information
- Information that is obtained about individuals other than the "target subjects," and whether such individuals meet the regulatory definition of "human subject" (e.g., a subject provides information about a family member for a survey)
- How to access the minimum amount of information necessary to complete the study

Confidentiality - methods used to ensure that information obtained by researchers about their subjects is not improperly divulged. Confidentiality refers to the researcher's agreement with the subject about how the subject's identifiable private information will be handled, managed, and disseminated. The research proposal should outline strategies to maintain confidentiality of identifiable data, including controls on storage, handling, and sharing of data. When appropriate, certificates of confidentiality could be used to maintain the confidentiality of identifiable data

When the IRB evaluates research proposals for strategies for maintaining confidentiality, where appropriate, consideration will be given as to whether:

- Methods to shield subjects' identity adequately protect subject privacy
- There is a long-range plan for protecting the confidentiality of research data, including a schedule for destruction of identifiers associated with the data
- The consent form and other information presented to potential research subjects adequately and clearly describe confidentiality risks.
- The informed consent process and the informed consent document, and if applicable the Authorization Form, clearly delineates who will have access to the subject's information and under what circumstances data may be shared (i.e., government agencies, sponsors).

53. Describe when and where subjects will provide their information. Include the nature of the information and who will receive and use the information. Document the provisions used to protect privacy interests of those subjects when gathering their information and data.

We will obtain the information from CPRS and from the subjects in an exam room or hospital room. We will obtain birthdate, PMH, and information on how to contact the person as the study is ongoing. The link to the code will be stored in a password protected file behind the VA firewall and in paper form in a locked cabinet in a locked room.

54. Will researchers have access to identifiable private information about potential subjects outside of this research project? *Ex. PI is provider who has access to medical records for clinical care*

- No **Yes- please explain:** The oncology CO-I's on the study are providers for the subjects.

55. Will Researchers collect identifiable private information on anyone other than the subject?

- *Ex. family members, friends, colleagues, classmates...etc.*

No Yes -please explain:

56. At the time data are transcribed or recorded for this study they are?

Fully identifiable- list identifiers to be collected:

Coded with a unique identifier- describe the code: It will be a few letters and numbers. We will not use the subjects S.S. number, birth date or initials for the code.

a. Who will have access to the key? All of the study team.

b. Where is the key maintained? Two locking barriers must be in place between the coded data and the key. We will have a password protected file behind the VA firewall and also a written backup stored in a locked drawer or cabinet in the oncology office area initially as the enrolment is ongoing and then for long term moved to [name] lab in K203.

De-identified-by Privacy Officer or Statistician.

Other (describe):

57. How will electronic research data be secured while the study is active?

No electronic data will be stored

VA encrypted laptop

Encrypted VA device/media- describe:

VA network drive;

M: drive; whose?

S: drive

Folder access password protected

Other drive location (for example P: drive):

Folder access password protected

58. How will hardcopy research data be secured while the study is active? Two locking barriers must be in place.

No hardcopy data will be stored

Locked office and locked file cabinet

Data coded by PI or study staff with a master list secured and kept separately

Data de-identified by Privacy Officer or Statistician- (VA does not consider coded data to be de-identified)

Other -specify:

59. Provide the physical location including room number (and address if outside of this VA) where all electronic and hardcopy data will be stored: A locked cabinet in the oncology office area ([name] office) and/or in [name] lab K203 in a locked cabinet.

60. Is identifiable information physically or electronically sent TO the LSCDVAMC from other institutions or locations?

- No Yes - contact Privacy Officer [name] or [name] [contact] / [contact] [contact] / [name] or Information Security Officer [name] [contact] / [contact] – prior to submitting to the Research Service.

